Aim 1: Validate the Marijuana Purchase Task (MPT) measure via administration to a representative sample of marijuana users and assessment of smoking behavior in the laboratory (*n*=85). Hypothetical MPT responses (e.g., how many hits of marijuana would you take if they cost \$0.25?, \$0.50?, etc...) will be compared to responses on an Actual MPT whereby one of the subject's response choices is selected at random to determine the amount of marijuana to be administered. Marijuana smoking topography will be assessed during a subsequent *ad libitum* smoking session.

- **Aim 1.1**: Test the hypothesis that performance on the Hypothetical MPT will be significantly associated with performance on the Actual MPT.
- **Aim 1.2**: Test hypothesis that marijuana craving post-administration will be lower than craving assessed pre-administration.
- **Aim 1.3**: Test the hypothesis that marijuana puff topography from the *ad libitum* marijuana self-administration session will be related to self-reported grams of cannabis used per week.

B.2. SAMPLE DESCRIPTION AND RECRUITMENT

Participants will be recruited from the community via flyers, advertisements, and social media. Potential subjects will be screened via phone and staff will summarize study procedures. Eligible subjects will be scheduled for an initial laboratory visit. Preliminary data suggests that there is much variability in marijuana use practices; therefore, we will include individuals with a range of use practices and patterns to capitalize on variability. During the initial laboratory visit, participants will provide informed consent and will be enrolled in the study using the following inclusion criteria:

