Aim 1 Approach. Laboratory Sessions: one experimental session (Session 1: controlled paced puff smoking procedure). Participants (n=85) will complete a baseline session with medical screening and two experimental sessions (Session 1: controlled paced puffing smoking procedure; Session 2: ad libitum smoking topography). Following phone screening, subjects will visit the laboratory to provide informed consent. They will be asked to refrain from all marijuana and tobacco smoking for 15 hours, alcohol for 24 hours, and caffeine for 4 hours prior to experimental sessions. Subjects will complete an alcohol breathanalysis, a urine drug screen and pregnancy test (females), and a carbon-monoxide (CO) reading to confirm absence of recent smoking. Subjects with a positive BrAC will be rescheduled. A positive THC screen will be required at this time to confirm marijuana status; however, positive results for other drugs will result in ineligibility. Participants who test positive for drugs other than marijuana will be given one re-try appointment. Participants that do not test positive for marijuana will not be given a re-try appointment. Those with a CO of > 8 ppm will be rescheduled due to the difficulty in confirming overnight marijuana abstinence with higher CO levels [7]–[9]. For those with a CO reading of more than 8ppm during the baseline session, research staff will consult with the PI on a caseby-case basis. PI discretion will be used to ensure the target CO reading of 8ppm is obtained. With respect to the experimental sessions, for those with a CO reading of more than 8ppm at session arrival, PI discretion will be used to ensure the target CO reading of 8ppm will be reached by the onset of marijuana administration. Participants will be allowed one re-test in the event of a CO level above the 8 ppm cut-off when the PI has determined the participant cannot feasibly reach a CO reading of 8ppm in a timely manner on the same date. Tobacco smokers will be allowed to smoke a cigarette following the CO test to prevent nicotine withdrawal. Similar CO-based procedures have been used in marijuana administration studies to avoid the onset of cannabis withdrawal [9]. Subjects will be administered a medical screening questionnaire to rule out history of adverse reaction to marijuana, and a structured clinical interview to rule out Axis I DSM-5 diagnoses. Ineligible subjects will be paid \$10 and excluded from further participation. Eligible subjects will complete baseline measures and undergo a medical screening exam to determine medical clearance prior to the marijuana administration sessions.

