
Drug: Marijuana (**5.9%** Δ^9 -tetrahydrocannabinol/THC) cigarettes will be provided by the NIDA Drug Supply Program. This dose was selected because administration of **5.9%** THC will closely model potency of marijuana obtained outside the laboratory as marijuana preparations have increased from 3.4% in 1993 to 8.8% in 2008 [10].

Laboratory Session 1: Controlled Paced Puff Smoking Procedure: Subjects will complete the Hypothetical (not associated with marijuana available to smoke) Marijuana Purchase Task (MPT), Actual MPT (identical to Hypothetical MPT but a response choice will be selected at random to determine amount of marijuana available to be smoked), and self-report measures of craving and subjective effects. A blood pressure cuff will be attached to continuously record heart rate (HR) and blood pressure (BP) during the entire experimental session for safety monitoring. Selection of marijuana amount available to smoke: A response choice corresponding to an item price will be randomly selected from the Actual MPT measure completed during the session. Subjects

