will draw a number and will be given a monetary budget based on the maximum price set on the MPT measure (\$20) for the marijuana smoking session. Once the response choice/price has been selected, the corresponding number of marijuana hits will be available to smoke, and the subject will receive any remaining money from the monetary budget (e.g., budget=\$20, item selected from Actual MPT =\$5/unit, subject reported he/she would purchase 3 units at this price, 3 units will be available during the smoking procedure, and subject will receive the remaining \$5 from the monetary budget). The controlled paced-puffing procedure [11] includes instructions to "light the cigarette" (30s), "get ready" (5s), "inhale" (5s), "hold smoke in lungs" (10s), and "exhale." The puffing sequence will continue until the subject chooses to cease smoking or the number of available units has been reached (i.e., 20 hits). Subjects are not required to smoke any marijuana as our intention is to assess the relationship between Actual MPT performance and real smoking in the laboratory. Subjects will be informed that the administration session will last 1-hour regardless of number of marijuana hits available. This methodology is based on established procedures that have been successfully used to assess demand for Hypothetical versus Actual alcohol [12]. No more than 20 hits total will be available during the session due to potential safety concerns (e.g., increases in HR which reliably occur [5], [13]).

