Security and Regulatory Aspects for Marijuana: Marijuana cigarettes will be provided by NIDA and will be stored frozen in an airtight container in a locked refrigerator safe located in a cement block room without windows and one door that is locked with code-protected card-key access at [name] on the 3rd floor. Only DEA designated individuals will have access to this room (located in the same building and floor as the location of marijuana administration). Thus, the cigarettes will remain secure at all times. [name] will retrieve a designated number of marijuana cigarettes prior to a scheduled experimental session, humidify them at room temperature for 24 hours before use (per NIDA's instructions) in the same cement block room, and transfer them directly to the laboratory following the start of the session.

Statistical Analysis Plan: The primary aim of this investigation is to confirm the validity of the Marijuana Purchase Task (MPT; primary outcome measure). A linear regression will be performed with marijuana hits purchased on the Actual MPT predicting marijuana hits actually purchased and smoked in the laboratory; baseline total individual income will be included as a covariate. The first secondary aim includes change in marijuana craving pre- and post-marijuana smoking during the experimental session (secondary outcome measure). A two-sided t-test will be conducted to compare craving pre- and post-marijuana smoking. The second secondary aim includes correlation between puffs on the topography device during *ad libitum* marijuana administration and self-reported grams of marijuana used per week (secondary outcome measure).

References

- [1] Office of National Drug Control Policy, "Marijuana Resource Center: State Laws Related to Marijuana | The White House." Accessed: Oct. 29, 2013. [Online]. Available: http://www.whitehouse.gov/ondcp/state-laws-related-to-marijuana
- [2] J. G. Murphy and J. MacKillop, "Relative reinforcing efficacy of alcohol among college student drinkers," *Exp. Clin. Psychopharmacol.*, vol. 14, no. 2, pp. 219–227, May 2006, doi: 10.1037/1064-1297.14.2.219.
- [3] J. J. Palamar, D. C. Ompad, and E. Petkova, "Correlates of intentions to use cannabis among US high school seniors in the case of cannabis legalization," *Int. J. Drug Policy*, Feb. 2014, doi: 10.1016/j.drugpo.2014.01.017.

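### Does the pre-post craving test need a stated rating time and a rule for participants who take no hits?

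*Combined protocol and SAP*

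**What the plan says.** Aim 1.2 (section B.1) sets the hypothesis that "marijuana craving post-administration will be lower than craving assessed pre-administration". The Statistical Analysis Plan at the end of section B.3 describes the outcome thus: "The first secondary aim includes change in marijuana craving pre- and post-marijuana smoking during the experimental session". The test is one sentence: "A two-sided t-test will be conducted to compare craving pre- and post-marijuana smoking". No significance level, effect size, SD, analysis set or rating time is given.

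The procedures name craving once, under Laboratory Session 1, in an untimed list that includes "self-report measures of craving and subjective effects". The same procedure allows no smoking at all: "Subjects are not required to smoke any marijuana as our intention is to assess the relationship between Actual MPT performance and real smoking". The hits on offer equal the participant's own answer at a randomly drawn price, so an answer of zero at that price also gives zero hits. Smoking has no fixed end: "The puffing sequence will continue until the subject chooses to cease smoking or the number of available units has been reached". The administration hour, however, has the same length for everyone.

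The Aim 1 Approach is inconsistent on the number of sessions. It opens with "one experimental session (Session 1: controlled paced puff smoking procedure" and then says participants "will complete a baseline session with medical screening and two experimental sessions".

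**The concern.** Two things that define a pre-post comparison are left open.

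The first is who is compared. A participant who took no hits has no state after smoking, yet may have two craving ratings. Counting such people changes what the mean difference estimates, and if the choice is made after the results are seen, the 5% error rate no longer holds.

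The second is when the later rating is made. Just after the last hit, at the end of the hour and before going home are different measurements. The Sobriety Assessment paragraph itself says that psychotropic effects wear off within 2-3 hours. An analyst can supply the pairing, but cannot change the time of a rating already collected.

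At stake is the interpretability of one of the three stated hypotheses. The primary validation of the purchase task is not affected.

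**Working it through.** The plan gives no figure for this test, so there is nothing to reproduce. The check is a reading of the text followed by illustrations on assumed values.

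**Reading.**
- *Paired or not.* The outcome is a change within the same people, so a paired test is the natural reading.
- *Session.* Craving is listed only under Session 1. Session 2 has an open-ended list of baseline measures, so Session 1 is a fair inference but not a certainty. The one-session and two-session wording in the Aim 1 Approach looks like a clerical remnant.
- *Set.* The SAP's phrase about craving after smoking, and the word administration in Aim 1.2, can be read as meaning those who smoked. No rule says so. The 85 is the planned sample.
- *Time.* The SAP places the change within the experimental session. The 3-hour stay has its own heading and follows the smoking procedure, so counting it as part of that session is doubtful.

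**Delay within the hour.** From the paced-puff timings, lighting takes 30 s and each hit at least 5 + 5 + 10 = 20 s (exhale and gaps are not given). Minimum smoking time is 30 + 20 × hits: 50 s for 1 hit and 430 s for 20. A rating at the end of the hour would come at most 3600 − 50 = 3550 s (about 59 min) after the last hit for a 1-hit participant, and at most 3600 − 430 = 3170 s (about 53 min) for a 20-hit participant.

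**Analysis set.** Assumed: all 85 rated, two-sided 5%, correlation r = 0.5, a fall of d SD in those who smoked, and zero mean change in the k who did not (share z = k/85).
- All participants: mean (1 − z)d, SD of change √(2(1 − r) + z(1 − z)d²), n = 85.
- At least one hit: mean d, SD √(2(1 − r)) = 1, n = 85 − k.
- Example, k = 19, d = 0.3: z = 0.224, mean 0.776 × 0.3 = 0.233, SD √(1 + 0.224 × 0.776 × 0.09) = 1.008.

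Power from the noncentral t distribution, all participants v at least one hit:

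| Zero-hit | d = 0.3 | d = 0.5 | d = 0.8 |
|---|---|---|---|
| 5 of 85 (6%) | 73 v 75-76% | 99 v 99% | >99% both |
| 19 of 85 (22%) | 56 v 67% | 93 v 98% | >99% both |
| 37 of 85 (44%) | 33 v 53% | 70 v 92% | 97 v >99% |

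**Direction.** Dilution depends on zero-hit participants not changing on average, which the documents do not say. If those who smoked do not change and 37 zero-hit participants fall by 0.3 SD, the overall mean fall is 37/85 × 0.3 = 0.13 SD, the SD is 1.011, and the test rejects about 22% of the time. Including them can therefore dilute a fall or produce one.

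**Choosing the set afterwards.** Simulating 100,000 trials with no change and rejecting if either set gives p < 0.05 yields about 6.1%, 7.2% and 8.1% for the three shares.

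**Rating time.** Assumed: everyone smokes, r = 0.5, and the fall shrinks linearly to zero at T = 2 or 3 hours, so fall = d(1 − hours/T). For d = 0.5 the fall at 1 hour is 0.25-0.33 SD and power drops from over 99% to 63-86%. At 2 hours it would be 0-0.17 SD and 5-33%, but only if the sobriety stay belongs to the session. The linear taper is an assumption, and the documents' 2-3 hours refers to psychotropic effects, not craving.

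**The case for a change.** The strongest case for a change is that two competent teams following this plan could rate craving at different times and analyse different people, and that a few sentences would prevent it at almost no cost. Zero hits are not a remote case. Prices run up to the whole $20 budget, so a high draw can leave a willing smoker with none. A rating time cannot be repaired once data are collected.

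Much of this stands. No time and no analysis set are stated, and writing them down would be good practice. What does not stand is the step from missing detail to a faulty analysis. Aim 1.2 asks only whether craving is lower afterwards, and a paired comparison answers that. Making all participants the lead analysis would not be a clear improvement either. It avoids selecting on behaviour after baseline, but it may run against the SAP's own wording and mixes in change unrelated to smoking. Restricting to those who smoked selects on demand and on the price drawn. Either set gives an uncontrolled pre-post change.

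**Conclusion.** The concern does not call for a change. It identifies detail the plan leaves out, with no rule shown to mislead. The ordinary reading is a paired two-sided t-test on Session 1 craving. Reporting the number who took no hits and the rating time actually used would let a reader judge the result. The choice of set is a fair trade-off.

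The consequences depend on figures absent from the documents. On the assumptions above, the choice of set costs little power if the fall is large (at least 97% in either set at 0.8 SD). It matters if the fall is small and many take no hits (33% v 53% at 0.3 SD with 37 of 85). Picking the set after seeing both results would raise the error rate from 5% to about 8% at most over the shares tried. The rating time is the part an analyst cannot supply, and it remains a real limit on interpretation. Its largest apparent effects rest on an assumed linear decline in craving and on treating the 3-hour stay as part of the session. For a secondary, uncontrolled comparison, that does not justify a required revision.

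### Does the pre/post craving t-test fall short because it cannot attribute the fall to marijuana and ignores the randomly drawn price?

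*Combined protocol and SAP*

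**What the plan says.** Aim 1.2 (B.1, Specific Aims) is the hypothesis that "marijuana craving post-administration will be lower than craving assessed pre-administration". The Statistical Analysis Plan defines the first secondary outcome as "change in marijuana craving pre- and post-marijuana smoking during the experimental session" and gives it one analysis: "A two-sided t-test will be conducted to compare craving pre- and post-marijuana smoking".

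Under Laboratory Session 1 (B.3, Methodology), participants complete both purchase tasks and "self-report measures of craving and subjective effects". The amount of marijuana on offer is then set by chance: "A response choice corresponding to an item price will be randomly selected from the Actual MPT measure completed during the session". The participant's own answer at that price fixes the number of hits, within a $20 budget and a cap of 20 hits, and "the subject will receive any remaining money from the monetary budget". Smoking is voluntary ("Subjects are not required to smoke any marijuana"). On timing, the section says: "Subjects will be informed that the administration session will last 1-hour regardless of number of marijuana hits available".

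**The concern.** All 85 participants are in a single group, with no placebo or no-smoking condition. The first craving rating follows a requested 15 hours without marijuana or tobacco, and tobacco smokers may have a cigarette after the carbon-monoxide test. Craving could therefore fall for reasons other than marijuana, and a pre/post test would register that fall. Some participants may smoke nothing and still have a later rating.

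The study also appears to hold an unused remedy. The price is random, it limits access to marijuana, and the session length does not depend on it. Regressing post-session craving on pre-session craving and the drawn price looks like a randomised comparison that needs no new data. If the trial meant to claim that marijuana lowered craving, it would be relying on the weaker analysis while ignoring the stronger one.

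**Working it through.** **Inputs from the documents.** Planned n = 85; budget $20; cap 20 hits; random price draw; one-hour administration session in Session 1.

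**Inputs assumed, because the documents do not give them.** Two-sided alpha 0.05; all 85 analysed; a paired test; pre and post ratings with SD 1 and correlation 0.5, so the SD of change is √(1 + 1 − 2 × 0.5) = 1. The full price list, the demand curve and the shape of any marijuana effect are also assumed.

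**1. What the t-test detects.** For a mean change of d SDs of change, the noncentrality is d√85 on 84 degrees of freedom.
- d = 0.2: 0.2 × 9.22 = 1.84, rejection 45%.
- d = 0.3: 0.3 × 9.22 = 2.77, rejection 78%.

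These rates apply whatever caused the change. They are not type I error rates for Aim 1.2: if craving has truly fallen by 0.3 SD, the hypothesis that it is lower afterwards is true, and rejecting no change is correct. The t-test would be at fault only against a causal hypothesis, and neither Aim 1.2 nor the analysis plan states one.

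**2. What the draw controls.** Maximum access is min(20, floor(20 / price)): 20 hits at $1, 4 at $5 and 1 at $20. The draw does vary access.

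**3. What the draw does not control.**
- *Time to the second rating.* The one-hour rule fixes the length of the administration session. The documents give no clock time for the post rating; they place it after smoking or after administration. Puffing ends when the participant stops or the hits run out. If craving is rated at that point, the interval between ratings grows with hits and so varies with price.
- *Knowledge of the draw.* Participants know the price, their hits and the cash left over before they give the post rating. Disappointment, money, the smoking ritual or expectancy could move that rating without any drug effect.

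**4. The price model when there is no drug effect.** The model is post = a + b × pre + c × log price, with 1 and 82 degrees of freedom. If price affects craving only through marijuana, it rejects in about 4–6% of simulated trials, as it should. Now let price shift the post rating by g SD per SD of log price through a non-drug route. The residual variance is 1 − 0.5² = 0.75, so the noncentrality is 85g² / 0.75.

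| g | Noncentrality | Rejection, formula | Rejection, simulation |
|---|---|---|---|
| 0.1 | 1.13 | 18% | 18% |
| 0.2 | 4.53 | 56% | 55% |
| 0.3 | 10.2 | 88% | 87% |

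The simulation used 4,000 trials per row and one assumed list of ten prices from $0.25 to $20. Other runs gave 18–19%, 53–55% and 87–88%. The size of g is an assumption, and it is scaled differently from the d in step 1, so the two sets of rates cannot be compared one for one.

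**5. The price model when marijuana does lower craving.** These ranges come from 2,000 simulated trials per scenario, over three assumed price lists and three assumed demand levels, with every purchased hit smoked.

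| Full drop (SD) | Effect levels off after a few hits | Effect linear up to 20 hits |
|---|---|---|
| 0.3 | 11–19% | 9–10% |
| 0.5 | 25–44% | 14–21% |
| 0.8 | 53–81% | 30–43% |

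Power of 80% needs a partial correlation of about 0.29. With a different assumed demand curve and drops of 0.10 to 0.15 SD per hit with no levelling off, power is 81–99%. The answer depends mainly on inputs that the documents do not supply.

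**The case for a change.** The best opposing argument is that readers may take a test of craving before and after smoking as evidence about marijuana, that the drawn price is the only randomised element in the study, and that using it costs one model. It is also a better choice than a model on hits smoked. Hits reflect each person's own demand, and under an assumed link between demand and non-drug change the hits model rejected in 27–30% of trials with no drug effect, against 4–5% for price.

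Much of this stands. The t-test carries no causal information, the draw is unused for craving, and price is preferable to hits. An analyst could reasonably add the model as exploratory. Rating craving before the draw would keep the price out of the pre rating, but no rule on the pre rating removes the route through the post rating in step 4. A significant slope would remain ambiguous, and for moderate effects a null slope would usually be uninformative.

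Some wording is also thin. The analysis plan does not use the word paired, it refers to a single experimental session although two are planned, and it gives no rating times. Pairing would matter if it were ignored: for a fall of 0.3 craving SD at correlation 0.5, power would be about 50% unpaired against 78% paired. But the outcome is defined as a change within the session, which points to a paired test, and craving ratings are named only under Session 1. These are details an analyst would fill in from the text.

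**Conclusion.** The concern does not hold. The planned test matches Aim 1.2 as written. Its 45% and 78% rejection rates under a non-drug fall show what the test cannot say about cause, but the aim and the analysis plan do not ask it to say that. The alternative would not reliably supply the missing attribution: about 18% to 87% rejection with no drug effect when the draw itself shifts the post rating by 0.1 to 0.3 SD per SD of log price, and about 9% to 44% power for drops of 0.3 to 0.5 SD.

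These figures rest on n = 85, alpha 0.05, a pre-post correlation of 0.5 and assumed price lists, demand and effect shapes. The main reason does not depend on them: Aim 1.2 is a statement about before and after, and a pre/post comparison answers it. Craving is a secondary outcome, and the primary regression is unaffected.

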Laboratory Session 2. *Ad Libitum* Smoking Topography Procedure: Participants will complete baseline measures including the Hypothetical MPT, and will then complete a 1-hour *ad libitum* marijuana self-administration session for assessment of smoking topography. Marijuana cigarettes (5.9% THC) will be smoked through a handheld smoking topography device (CReSSMicroTM). The device will include a holder for the cigarette and study staff will place the cigarette in the device. The subject will light the cigarette and each puff will register immediately upon inhalation. Data from the device will be downloaded and indices of topography will be recorded including number of cigarettes, number of puffs, puff volume (ml), puff duration (ms), average puff velocity (ml/s), and time to peak velocity (ms). Logs will also be maintained by the PI and RA documenting number of puffs smoked and each cigarette or partial cigarette smoked ensuring an accurate count of marijuana cigarettes smoked during the session. These procedures have been successfully used to assess marijuana smoking topography [14]. A maximum of two joints will be available during the session.

Sobriety Assessment: Subjects will receive snacks upon the completion of the administration session. Subjects will remain in the laboratory for 3-hours following the smoking procedure (psychotropic effects of smoked marijuana taper off within 2-3 hours [15]), and will subsequently be evaluated for motor signs of intoxication. Following completion of a field sobriety test [16], subjects will be transported home in a taxi.

Compensation: Participants will be paid \$20 for the baseline session, \$10 for the physical exam, and \$50 for each experimental session (and amount remaining from \$20 tab) for a total of at least \$130 and up to \$150.

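### Does correlating only puff count with grams per week, by an unnamed coefficient, undermine the test of Aim 1.3?

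*Combined protocol and SAP*

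**What the plan says.** Section B.1, Aim 1.3, reads "Test the hypothesis that marijuana puff topography from the" ad libitum session "will be related to self-reported grams of cannabis used per week". The aim names no single index.

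Section B.3, Laboratory Session 2, says that "indices of topography will be recorded including number of cigarettes, number of puffs, puff volume (ml), puff duration (ms"), followed by average puff velocity and time to peak velocity. That makes six indices, with number of puffs and puff volume listed separately. Staff keep a second record of two of them: "Logs will also be maintained by the PI and RA documenting number of puffs smoked and each cigarette or partial cigarette smoked". The session has a ceiling: "A maximum of two joints will be available during the session".

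The Statistical Analysis Plan paragraph at the end of B.3 then specifies: "The second secondary aim includes correlation between puffs on the topography device during" ad libitum administration and self-reported grams per week, as a secondary outcome. It states no coefficient, sidedness or transformation for this analysis. None of the other five indices is assigned to an analysis.

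Section B.2 says of recruitment that "we will include individuals with a range of use practices and patterns to capitalize on variability".

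**The concern.** The aim is broad and the analysis is narrow. Puff count mixes how much is smoked with how large each puff is. Two people who draw the same total volume have different counts if their puff sizes differ. For anyone who finishes both joints, the count mainly reflects puff size. If that dilution were material, a weak or null result could not be told apart from a poor choice of index, although the volume data that might separate the two are already collected.

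The unnamed coefficient adds to the worry. A sample recruited for its range of use may well have skewed grams per week, and Pearson and Spearman correlations can then behave quite differently. Leaving the choice open also allows it to be made after the data are seen.

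**Working it through.** **Inputs.** From the documents: n=85, the six indices and the two-joint maximum. The documents give no power, alpha or expected correlation for this aim. They also give no puff-size spread, device error, share of participants reaching the limit, or correlation of puff size with anything. There is therefore no plan figure to reproduce, and every other input below is an assumption. Alpha is taken as 0.05 two-sided.

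**Step 1: closed form, no ceiling.** On the log scale, count C = V − S, with V total volume and S mean puff size. Let G be grams per week and k = SD(S)/SD(V). Then

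corr(C,G) = (rVG − k·rSG) / √(1 + k² − 2k·rVS).

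Power is approximately Φ(atanh(r)·√82 − 1.96). Take rVG = 0.30, for which power is 80%, and k = 0.5:

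- rSG = 0, rVS = 0: 0.30/√1.25 = 0.268, power 70%.
- rSG = +0.15, rVS = 0: 0.225/√1.25 = 0.201, power 46%.
- rSG = −0.15, rVS = 0: 0.375/√1.25 = 0.335, power 89%.
- rSG = 0, rVS = 0.3: 0.30/√0.95 = 0.308, power 82%.

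When rSG = 0, count equals error-free volume at rVS = k/2, which is 0.25 here. Above that value, count does better.

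**Step 2: device error.** If recorded volume carries independent log-scale error with SD equal to e·SD(V), its correlation with G is 0.30/√(1 + e²). With rSG = rVS = 0, count gives 0.30/√(1 + k²). The two are equal when e = k, so volume loses its advantage once device error matches the spread in puff size.

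**Step 3: simulation with the two-joint ceiling.** Assumptions: log intake SD 0.5, correlated 0.30 with log grams; 20% of participants at the limit; puff-size CV 40%; amount smoked taken to equal total drawn volume. There were 4,000 or 6,000 trials per row. Entries are mean Spearman correlation (power).

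| Puff size with grams | Puff size with amount | Puff count | Volume, no error | Volume, error log-SD 0.2 |
|---|---|---|---|---|
| +0.2 | 0 | 0.07 (9%) | 0.28 (76%) | 0.25 (64%) |
| 0 | 0 | 0.20 (46%) | 0.28 (75%) | 0.25 (65%) |
| 0 | 0.3 | 0.24 (61%) | 0.28 (75%) | 0.25 (64%) |
| 0 | 0.5 | 0.28 (75%) | 0.28 (74%) | 0.25 (62%) |
| −0.2 | 0 | 0.33 (88%) | 0.28 (74%) | 0.25 (65%) |

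Small differences down the volume columns are simulation noise. In the second row, raising device error to 0.4 brings volume to 0.20 (45%), level with count. This agrees with step 2: a CV of 40% is a log-SD of √ln(1.16) = 0.385, close to 0.4. With CV 20%, correlation of puff size with amount 0.3 and device error 0.2, count gives 0.28 (75%) and volume 0.25 (63%). Cigarettes smoked, to the nearest half and without error, gives 0.27 (71%) under the second row's assumptions, which is above volume with error 0.2.

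**Step 4: the coefficient.** With a latent correlation of 0.30, lognormal grams and no ceiling, Pearson power is 70%, 58% and 46% at log-SD 0.5, 1.0 and 1.5. Spearman power is about 76% throughout. With a ceiling binding at the median, Pearson gives 62%, 43% and 24%, and Spearman 68% to 69%.

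**The case for a change.** The strongest case for a change is that it costs only wording. The data are already recorded. Naming one index and one coefficient in advance would prevent a choice among six indices and several coefficients once results are known. If heavier users take larger puffs, count could nearly lose the signal (0.07 in the table). If they take smaller ones, count overstates the link with amount smoked. On either reading, count alone cannot say whether a result reflects amount or puffing style.

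Part of this stands. Count can be pushed up or down by puff size, and the coefficient is not named; step 4 shows that the choice could matter if grams per week is strongly skewed.

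The step to making volume the main measure does not stand. The model behind step 3 favours volume by construction: it equates drawn volume with amount smoked and fixes the 0.30 correlation on that quantity. Nothing in the documents says the two are equal. Volume also meets the same two-joint ceiling and has no second record, whereas puffs and cigarettes are logged by staff as well. As to choice after the fact, the plan already commits to puffs, and keeping to one index limits multiplicity.

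**Conclusion.** No change to the plan is needed. The aim and the analysis do not conflict: the protocol counts number of puffs among its topography indices, and the plan tests that one. Moving to volume is a trade-off without a demonstrated gain. At device error 0.2, CV 40% and 20% at the limit, count minus volume in mean rank correlation runs from 0.07 − 0.25 = −0.18 to 0.33 − 0.25 = +0.08. Its sign depends on correlations of puff size with use and with amount smoked, and the documents give neither.

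The unnamed coefficient is missing detail, not a wrong rule. The text does not commit the analyst to Pearson on raw grams, and a rank correlation or a log transformation is the usual response to a skewed variable. Reporting volume, cigarettes smoked and the number of participants who used both joints alongside count would be useful, but it is optional and corrects no result.

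This is the second of two secondary outcomes, and the primary analysis of the purchase task is unaffected. The conclusion would need another look if pilot data showed that heavier users take clearly larger puffs and that device error is small.
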